**A Feasibility Study: Understanding and Altering Pain Expectations in Subjects with
Osteoarthritis of the Knee or Hip**

11/6/2014

NCT02155257

Why a feasibility study

In May we submitted a Program Project Grant (P01) application to the NIH. This \$10 million effort would fund a group of laboratory and clinical investigations to better understand and prevent the problem of chronic pain and disability after major surgery. Although we provided some preliminary data with that application, we expect that additional feasibility data will be required for the application to reach a level of priority high enough for funding. The current IRB application is to collect those feasibility data in time for a November, 2014 revision.

Both chronic pain and disability after total knee replacement surgery are predicted by negative cognitive-affective state, characterized by depression, anxiety, and a cognitive style dominated by catastrophizing. How this negative state results in chronic pain and disability is not known, but we hypothesize that it causes dysfunction of the release of the neurotransmitter, norepinephrine in several regions of the brain, mid-brain, and spinal cord that are important to many processes involved in recovery from surgery. In the P01 grant application we propose to test these circuits in animals and to study patients after total knee replacement as well as those with moderate daily pain and osteoarthritis who are not undergoing surgery. This protocol is to generate feasibility data for the osteoarthritis study in time for the Nov, 2014 revision, if it is needed.

Background

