Expectations alter pain experience. We are also manipulating expectations in this study of healthy volunteers. Pain stimuli are first presented as a random series without cues, then as a series preceded by 6 sec with an auditory cue to indicate whether the stimulus would be mildly (47°C) or moderately (50°C) painful, then as a series with 20% of the cues incorrect. So far we have observed a mild, but highly significant reduction in pain from random to cued condition, consistent with a recent report on the role of uncertainty in pain reporting (Yoshida, 2013). During miscuing, there was a greater effect of negative expectations (expect less pain) than positive ones (expect more pain), as previously reported (Koyama, 2005). In the proposed

[figure not shown]

Figure 2: Time course of heat stimulus and of VAS and pupil responses

[figure not shown]

Figure 3: Relationship between resting pupil diameter and pain reporting by affective distress

study we gather feasibility data in a clinical population (patients with moderate osteoarthritis of the hip or knee) to test whether we can manipulate expectations on pain in this population.

Gabapentin and modafinil to increase LC activity and gain. In animals and humans, the alertness enhancing drug, modafinil (Provigil™) increases tonic LC activity and increases pupil diameter. Although large doses of this drug (800 mg) can increase blood pressure and heart rate, this has not been observed in these studies of over 100 people who received 200 mg (Hou, 2005; Nikolaou, 2008; Minzenberg, 2008; Schmaal, 2013; Geng, 2013). For this reason, we will examine the effects of modafinil, 200 mg, on pupil diameter and its effect to alter pain reporting as a function of baseline state by increasing gain.

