A more relevant drug to the question of chronic pain after surgery is gabapentin, and some clinical trials have suggested that perioperative treatment of this drug can reduce the incidence of this problem (Schmidt, 2013). In the NIH application we propose to test gabapentin rather than modafinil because our previous work with direct measures in rats and cerebrospinal fluid norepinephrine sampling in humans is consistent with gabapentin activating LC in both species (Hayashida, 2007). The pupil measurements in this feasibility study will more directly assess whether gabapentin does indeed increase LC activity in humans. Should it fail to demonstrate a reasonable effect size to dilate the pupil, we will revise the NIH application to study modafinil rather than gabapentin. As such, these preliminary data are very important to the design of the final study.

Study Design.

Hypotheses: (1) Gabapentin and modafinil will increase resting pupil diameter with a moderate effect size in patients with osteoarthritis; (2) Expectations will modify pain experience with a moderate effect size in these patients

Study design: Single-center, randomized, controlled study of gabapentin, modafinil, and placebo in 30 subjects (10 per group) with moderate osteoarthritis pain of the hip or knee or healthy individuals without pain

Primary outcome measures: (1) Resting pupil diameter and response to noxious stimuli after study drug; (2) Interaction between resting pupil diameter and correlation of cognitive-affective state to pain reporting.

Inclusion criteria: Adult, nonpregnant adults scheduled with moderate pain (verbal score of $\geq 4 \leq 7$ on 0-10 scale for average pain intensity with normal activity) from osteoarthritis of the knee or hip, or healthy individuals without pain, American Society of Anesthesiologists physical status 1-3, able and willing to perform the study procedures, including sitting in a chair for 45 min. Individuals must be able to read.

Exclusion criteria. (1) Inability to complete questionnaires; (2) Pregnancy; (3) Currently taking gabapentin or > 50 mg morphine equivalents/day; (4) advanced or unstable cardiac, pulmonary, renal or hepatic dysfunction; (5) history of previous eye surgery; (6) psychotic disorder or a recent psychiatric hospitalization.

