Catastrophizing-Optimism continuum assessment. Prior to the initiation of experimental procedures, each participant will be administered the battery of questionnaires Table 1. From these questionnaires, we will place each participant on a dimensional continuum that describes their general cognitive style. We will use multidimensional scaling (MDS) to force catastrophizing and optimism as 2 ends of this continuum (Figure 4). These two constructs

describe cognitive styles that are strongly inversely associated with each other; MDS will provide the optimal weights to best order individuals on this latent scale. Studies have examined the interplay of these constructs with other psychological concepts such as acceptance, pain-related disability and psychosocial adjustment and have found that both are reliably associated with the positive and negative aspects of the adjustment to pain.

Study procedures: A total of 30 subjects with moderate average daily pain from osteoarthritis of the knee or hip or subjects with no pain will be recruited and will come to the clinical research unit at Wake Forest. Informed consent will be confirmed and they will complete the questionnaires. We will take a verbal medical and medication history and obtain blood pressure and heart rate measurements. Verbal pain intensity report (0-10 from no pain to worst pain imaginable) will be obtained from 5 sec heat stimuli, separated by 30 sec, delivered to a nonpainful area of skin on the arm as described in preliminary data. During pain testing, study subjects will sit in a comfortable chair in a low-ambient light room with their head positioned on a chinrest for continuous recording of pupil diameter using a near infrared recording system as described in preliminary data. Pupil diameter and probe temperature will be passed through an analog to digital converter and acquired at 60 Hz for subsequent analysis.

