Data analysis. Pupil diameter data will be conditioned to remove blink and saccade artifacts and smoothed using an autoregressive filter. The local resting diameter will be determined representing the average smoothed value for the 500 msec preceding the stimulus onset. The pupil response to each stimulus is calculated as the mean pupil diameter during the 5 sec stimulus after accounting for lag time from onset of stimulus to onset of pupil response and is expressed as a % change from the local resting diameter (see our preliminary data for examples). Multidimensional Scaling (MDS) will be used to create a single dimensional scale from the catastrophizing and optimism scores (i.e., responses from these two questionnaires will be weighted and scaled to create a single-dimensional construct)

To determine the interaction among the factors of interest, and to accommodate the many repeated measures within each participant, we will utilize Generalized Estimating Equations. In our experience, the pupil response to painful stimuli is well modeled by a normal distribution with an identity link and an AR1 repeated measures covariance structure. To examine our hypotheses, we will model percent pupil change (the DV) using fixed effects for stimulus temperature, catastrophizing-optimism score (i.e., cognitive-affective state), and pre-stimulus baseline pupil diameter (i.e., LC activity). The association between cognitive-affective state and pain reporting will first be examined, and in a later block the moderating effect of baseline pupil size will be entered.

The goal of this feasibility study is to estimate the effect size of drugs on pupil diameter and the strength of interaction between pupil diameter and the relationship between cognitive-affective state.

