Expected results. We anticipate, based on preliminary data, that pain reporting will be weakly correlated with cognitive-affective state and that resting pupil diameter as a reporter of LC gain will interact with this correlation or tendency to apply cognitive style to pain reporting. We anticipate overall reduced pain reporting after placebo (placebo effect) and that the magnitude of this reduction and that of negative of pain will be inversely related to location on the optimism-catastrophizing continuum (i.e., greater placebo effect, greater effect of negative expectations of pain, and lesser effect of positive expectations of pain in strong optimists). After gabapentin or modafinil we anticipate that resting pupil diameter will be greater (i.e. greater tonic LC activity) than placebo. According to the gain concept, the effect of gabapentin on pain reporting across conditions should depend on cognitive-affective state, with overall reductions in pain reporting in strong optimists and amplification of pain in strong catastrophizers. The study is not powered to definitively show the effects of these drugs on either pupil diameter or its relationship to pain reporting as a function of optimism-catastrophizing. Rather, it is to provide feasibility, effect size, and variability data to support the choice of drug and power analysis for the eventual controlled study.

References

1. Alexander, JK, et al. Beta-adrenergic modulation of cognitive flexibility during stress. *J Cogn Neurosci* 2007;19:468-478.
2. Astafiev, SV, et al. Comment on "Modafinil shifts human locus coeruleus to low-tonic, high-phasic activity during functional MRI" and "Homeostatic sleep pressure and responses to sustained attention in the suprachiasmatic area". *Science* 2010;328:309-
3. Chapman, CR, et al. Phasic pupil dilation response to noxious stimulation in normal volunteers: relationship to brain evoked potentials and pain report. *Psychophysiology* 1999;36:44-52.
5. Geng, JJ, et al. A match made by modafinil: probability matching in choice decisions and spatial attention. *J Cogn Neurosci* 2013;25:657-669.
6. George, SA, et al. Altered locus coeruleus-norepinephrine function following single prolonged stress. *Eur J Neurosci* 2013;37:901-909.

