A Feasibility Study: Understanding and Altering Pain Expectations in Subjects With  
Osteoarthritis of the Knee or Hip  
Statistical Analyses Plan

NCT02155257

11/02/2018

To address the two primary hypotheses, linear mixed effects models will be employed. For each model, subject will be specified as a random effect to account for the repeated measures within individuals. To examine the impact of drug (i.e., placebo, gabapentin, modafanil) on tonic pupil diameter, pupil diameter will be regressed on fixed effects for drug, time (i.e., pre-drug vs post-drug), and a drug x time interaction. A group x time integration would be interpreted as evidence supporting the hypothesis that drug differentially impacted baseline pupil over time.

To examine the impact of tonic pupil diameter on the relationship between cognitive style (i.e., catastrophizing-optimism dimension) and pain reporting, VAS scores will be regressed on fixed effects for catastrophizing-optimism, tonic pupil diameter, and the interaction between catastrophizing-optimism x pupil diameter. A statistically significant interaction would be interpreted as evidence that tonic pupil diameter moderated the relationship between cognitive style and pain reporting. Where appropriate, all analyses are two-tailed with statistical significance interpreted at  $p < 0.05$ . The analyses will be conducted using R 3.4 and R Studio.

The sample size was based on estimating the feasibility of the protocol and on establishing effect size estimates. No formal statistical power calculations were conducted.

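### The hypotheses concern osteoarthritis, but pain-free people may fill any of the 30 places, and no planned analysis separates or adjusts for the two groups

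*Protocol*

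**What the plan says.** **Target population.** Protocol, Why a feasibility study: "This protocol is to generate feasibility data for the osteoarthritis study". Hypothesis 1 (Protocol, Study Design) reads "Gabapentin and modafinil will increase resting pupil diameter with a moderate effect size in patients with osteoarthritis", and hypothesis 2, on expectations, refers back to the same patients. The Background describes the aim as to "gather feasibility data in a clinical population (patients with moderate osteoarthritis of the hip or knee").

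**Enrolled population.** The Study design entry describes a three-arm randomised comparison "in 30 subjects (10 per group) with moderate osteoarthritis pain of the hip or knee or healthy individuals without pain". The inclusion criteria repeat the alternative, and Study procedures gives "A total of 30 subjects with moderate average daily pain from osteoarthritis of the knee or hip or subjects with no pain". No number or minimum share is set for either group, and the randomisation text mentions no stratification.

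**Analysis.** In the SAP's drug model, "pupil diameter will be regressed on fixed effects for drug, time (i.e., pre-drug vs post-drug), and a drug x time interaction", with subject as a random effect. Its second model regresses pain score on cognitive style (the catastrophizing-optimism score), tonic pupil diameter and their product. The protocol's Data analysis section uses temperature, style and baseline pupil diameter, and adds: "The association between cognitive-affective state and pain reporting will first be examined". None of these models contains osteoarthritis status, and no estimate by status is planned.

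**Use of the result.** Expected results: "to provide feasibility, effect size, and variability data to support the choice of drug and power analysis for the eventual controlled study".

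**The concern.** As written, thirty patients, thirty healthy volunteers or any mixture would satisfy the plan. The effect size taken forward to the drug choice and the power analysis would come from a population that the plan never defines. Without a split by status, a reader could not tell whether it applies to osteoarthritis.

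The pain model raises a second, narrower issue. Style and pupil size are not randomised. If patients and healthy people differ in both style and reported heat pain, pooling them can produce a style-pain association that exists in neither group.

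**Working it through.** **Inputs from the documents:** 30 subjects, 3 arms of 10 (3 × 10 = 30, as stated); two-sided 0.05; no power calculation. The documents give no SD, no numerical effect size, no expected mix and no patient-healthy comparison, so every difference by status below is assumed.

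**1. Drug effect.** Read a moderate effect as d = 0.5 in osteoarthritis (assumption). With osteoarthritis share p and a common SD, pooled d = p × 0.5 + (1 − p) × d(healthy). At p = 0.5:
- d(healthy) = 0.5: pooled d 0.50, no shift
- d(healthy) = 0.25: pooled d 0.375, shift 0.125
- d(healthy) = 0: pooled d 0.25, shift 0.25

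**2. Precision.** The 95% half-width for one drug against placebo, in SD units, is √(2/n) × t(0.975, 2n − 2):
- n = 10 per arm, pooled: 0.447 × 2.101 = 0.94
- n = 5 per arm, osteoarthritis only: 0.632 × 2.306 = 1.46

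On change scores with an assumed pre/post correlation of 0.8, multiply by √(2 × 0.2) = 0.632, giving 0.59 and 0.92. The largest shift above, 0.25, is inside the pooled half-width on either scale.

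**3. Should the osteoarthritis estimate replace the pooled one?** Take the extreme case (0.5 against 0, p = 0.5) and compare root mean squared error for the osteoarthritis effect. With change-score variance v = 2(1 − ρ), pooled is √(0.25² + 0.2v) and osteoarthritis-only is √(0.4v).
- ρ = 0.5: 0.51 v 0.63
- ρ = 0.8: 0.38 v 0.40
- ρ = 0.9: 0.32 v 0.28

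They are equal at v = 0.0625/0.2 = 0.3125, that is ρ = 0.844. Below that the pooled estimate is closer to the osteoarthritis effect even in this extreme case.

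**4. Style-pain association.** Let style and pain each be shifted by δ SD between groups at 50:50, with no association within groups. Each variance is 1 + δ²/4 and the covariance is δ²/4.
- δ = 1: r = 0.25/1.25 = 0.20. Fisher's z gives 0.203 × √27 = 1.05, so the rejection rate is about 18%.
- δ = 0.5: r = 0.0625/1.0625 = 0.059, rejection about 6%.

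Simulation (n = 30, one record per subject) gives 19-20% and about 6% for a style-only model. A status main effect returns the first to about 5%.

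**5. SAP pain model, same δ = 1 setting.** With a product term present, the style coefficient is the slope at pupil diameter zero. With pupil diameter centred it rejects in about 18% of runs; with pupil diameter uncentred, its mean an assumed 4 SD above zero, in about 5%. The SAP does not mention centring. The style by pupil test rejects in about 4-5%.

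**6. Chance allocation without stratification**, three arms of 10 (hypergeometric). With 6 osteoarthritis subjects, some arm has none in 19.5% of allocations. With 10, some arm has two or fewer in 70%; with 15, in 7.5%.

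**The case against.** The case for leaving the plan alone is substantial.

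- The study says that it is not powered for definitive drug effects. It also asks whether gabapentin raises locus coeruleus activity in humans, which healthy people can inform. This stands: enrolling a mix is not in itself a fault.
- A reader might infer that the pooled drug effect is biased or that the next trial will be wrongly sized. The documents do not support that. Drug is randomised, a stable pupil difference between groups largely drops out of drug x time, and no difference in drug response by status is shown.
- A reader might infer that the moderation analysis is invalid. Primary outcome 2 and the SAP's stated inference are both the interaction, which stays near its nominal level unless the style slope differs by status. The exposed result is a preliminary step that the protocol expects to be weak.
- Calling the 19-20% a false-positive rate would be too strong. In the enrolled mix the association is real; it is misleading only if read as holding within patients or within healthy people.
- A 1 SD shift in pain has no basis in the documents. The outcome is report of heat on a nonpainful area of the arm, not arthritis pain.
- The simulations use one record per subject, whereas the SAP model has repeated measures with pupil diameter varying within subject. Standard errors and power for the interaction cannot be carried over, and none are used here.

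These points limit the harm. They do not answer the gap that the plan never says which population its effect size describes.

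**Conclusion.** The point holds as a mismatch between the stated population and the analysed one. Exact adherence to the plan would carry a pooled effect of unknown composition into the drug choice and the next power analysis. Whether that effect differs from the osteoarthritis effect is unknown, and any plausible shift is small beside the sampling error.

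The confounding concern is conditional. It applies to the style-pain association in a style-only step, or in the SAP model if pupil diameter is centred. It needs shifts nearer 1 SD than 0.5 SD in both variables, at a roughly even mix.

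Nor do the figures support restricting the analysis to osteoarthritis subjects. The change is worth making because it is nearly free and aligns the output with the hypotheses, not because the planned tests are unsound.

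**What to change.** 1. Report osteoarthritis and healthy counts per arm. Give each drug-placebo pupil effect with its confidence interval in osteoarthritis subjects beside the pooled estimate, say which population each describes, and state in advance which one feeds the power calculation. Where an arm has too few osteoarthritis subjects, keep that estimate descriptive. Give the same split for the expectation effect in hypothesis 2.
2. In the pain model, centre pupil diameter and add status as a main effect. Show results with and without status, because osteoarthritis may itself contribute to cognitive style and adjustment could remove part of the association of interest. A main effect does not deal with a style slope that differs by status.
3. If enrolment is still open, stratify randomisation by status. If it is complete, make the analysis changes alone.

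**Cost.** One table and one model term; status is already known from eligibility, and no extra subjects or measurements are needed. The drawback is precision: at 5 per arm the osteoarthritis-only half-width is about 1.46 SD, against 0.94 SD pooled at 10 per arm. That estimate should therefore sit beside the pooled one and not replace it.

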In this ongoing study we have examined pupil responses to phasic noxious heat stimuli to date in 19 normal volunteers and 4 subjects with migraine (but not in the presence of a headache). Studies were performed in a room with constant, low ambient light so that both constriction and dilation of the pupil could be observed. Pupil diameter was continuously monitored by an infrared camera (Eye-Trac™ system; Applied Science Laboratories) with the subject's chin resting on a chin rest and gaze on a fixed object presented on a monitor. A 4 cm² Peltier-controlled thermode was placed on the calf, with temperature maintained at 35°C and 5 sec stimuli at various temperatures applied every 30 sec. Subjects reported pain intensity with a visual analog scale (VAS) from 0 (no pain) to 100 (worst pain imaginable). Increasing probe temperature to 50°C resulted in pain report and pupil dilation, the former with a longer lag (Figure 2, typical response). As previously described with other stimuli (Chapman, 1999; Oka, 2007), there was a direct relationship between pupil dilation and noxious heat temperature as well as VAS pain intensity and unpleasantness.

We next examined the relationship between pupil response and pain report as a function of affective distress. We estimated affective distress as the sum of scores to the pain catastrophizing scale, the CSED depression scale, the state trait anxiety inventory, and the pain anxiety symptom scale and linearly regressed this on pain report. The residual from the regression line for each individual was related to baseline pupil diameter as a measure of tonic LC activity. Despite there being a very small range of affective distress in this largely normal population, the residual (tendency to adhere to cognitive-affective state in pain reporting) was significantly related to baseline pupil diameter (Figure 3).

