Five sequences of test stimuli will be presented, with a brief break in between each sequence (Figure 5A). The first sequence will consist of 7 stimuli, from 39° to 51° C in 2° C increments, in ascending order. Data from this training sequence will not be used for analysis. Sequences 2 and 3 will consist of 5, 5-sec stimuli, presented in random order, to generate moderate (50° C) and mild (47° C) pain (random condition). Sequences 4 and 5 will also consist of random presentation of 5 stimuli at these temperatures, but with different auditory tones 6 s prior to stimulus onset to correctly cue the stimulus temperature (cued condition).

Subjects will then be randomized to receive oral gabapentin, 900 mg, modafinil, 200 mg, or placebo, followed 2 hr later by pain testing with pupillometry, consisting of different sequences (Figure 5B). The random and cued paradigms will be presented twice each (only 1 representative shown in Figure 5B), followed by a sequence with one miscue in the positive expectation for pain direction (signal for 50° C but deliver 47° C) and one in the negative

Table 1. Questionnaires

Stanford Expectations of Therapy Scale
WOMAC- Osteoarthritis Index
Life Orientation Test-Revised (LOT-R)
PROMIS- Depression
PROMIS- Anxiety
Pain Medication Attitudes Questionnaire (PMAQ)
Pain Locus of Control Scale (PLOC)
Pain Self-Efficacy Scale (PSE)
Barratt Impulsivity Test
Fear of Pain Questionnaire
Pain Catastrophizing Scale (PCS)
Tampa Scale of Kinesiophobia (TSK)

[figure not shown]

Figure 4: The dimensional structure of the continuum of cognitive style to be used, including psychosocial constructs associated with each end.

expectation for pain direction (mistrust condition, yellow bars in Figure 5B). Subjects will provide verbal pain intensity scores after each stimulus.

The pre-drug and post-drug set of sequences will take approximately 30-40 min including breaks between sequences of stimuli. Following this subjects will be discharged from the clinical research unit accompanied by a responsible adult.

[figure not shown]

Figure 5: Heat stimuli give before (A) or after (B) study drug

Subject payment. Subjects will be paid \$250 for participation in the study.

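### On cued trials the only defined resting-pupil window falls 5.5 to 6.0 s after the temperature tone; used trial by trial, it could carry anticipation into the style-by-pupil pain model

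*Protocol*

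**What the plan says.** **Window.** Protocol, Data analysis: "The local resting diameter will be determined representing the average smoothed value for the 500 msec preceding the stimulus onset". No exception is made for cued or miscued trials, and neither document defines another resting, baseline or tonic window. The same section names as a model term "pre-stimulus baseline pupil diameter (i.e., LC activity", so the pre-stimulus value is read as locus coeruleus activity. That model does include stimulus temperature, but its outcome is percent pupil change, not pain.

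**Tone.** Protocol, Study procedures: the cued sequences are run "with different auditory tones 6 s prior to stimulus onset to correctly cue the stimulus temperature (cued condition". The lead is not restated for the post-drug mistrust sequence. Background, on the earlier volunteer study, describes cueing "then as a series preceded by 6 sec with an auditory cue".

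**Pain model.** SAP, second paragraph: "VAS scores will be regressed on fixed effects for catastrophizing-optimism, tonic pupil diameter, and the interaction between catastrophizing-optimism x pupil diameter". Subject is a random effect and tests are two-sided at 0.05. The SAP does not say which window or trials supply tonic diameter, or whether it enters per trial or as a mean.

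**Role.** The second primary outcome in the protocol is "Interaction between resting pupil diameter and correlation of cognitive-affective state to pain reporting".

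**The concern.** On a cued trial the subject has known for more than 5 s which temperature is coming when the resting value is taken. If the pupil is still wider after the high tone, that value mixes tonic state with anticipation of a known stimulus.

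The pain model contains neither temperature nor cue. On correctly cued trials a tone-driven change in pupil size therefore also marks the temperature delivered. If people of different cognitive style (their place on the catastrophizing-optimism scale) differ in how much temperature or cue changes their pain rating, part of that difference can be attributed to style by pupil. The interaction could then look like moderation by tonic activity when there is none.

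The protocol makes estimating this interaction a goal of the study and says the results will support the power analysis of the eventual controlled study. A biased estimate would carry over into that design.

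**Working it through.** The plan states no power, effect size or SD for this test, so there is no design figure to reproduce.

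**1. Timing.** Tone at -6.0 s; window from -0.5 to 0 s. After the tone: 6.0 - 0.5 = 5.5 s to 6.0 s. At 60 Hz this is 0.5 x 60 = 30 samples.

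**2. Trials affected.** The training sequence is not analysed.
- Pre-drug: 2 x 5 uncued and 2 x 5 cued, so 10 of 20.
- Post-drug: 10 uncued, 10 cued and one mistrust sequence of unstated length. Assuming 5 stimuli and a 6 s lead, 15 of 25.
- Overall: 25 of 45 (56%). With 0 to 10 mistrust stimuli, 20 of 40 to 30 of 50 (50% to 60%).

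**3. Size of the bias by hand.** SAP model: pain = b0 + b1 S + b2 P + b3 S x P + subject effect + error, with S style and P pupil, both in SD units (within-subject SD for P). Let the true b3 be 0, code temperature T as +0.5 or -0.5, let its effect vary with style by g points per SD, and let a high tone widen the pupil by d. With 23 correctly cued and 2 miscued tone trials in 45:
- within-subject covariance of T and P = 0.25 x (23 - 2)/45 x d = 0.117d
- within-subject variance of P = 1 + d² x (12.5/45) x (32.5/45) = 1 + 0.20d²
- spurious b3 is about g x 0.117d / (1 + 0.20d²)

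For g = 0.5 this gives 0.014, 0.028 and 0.049 at d = 0.25, 0.5 and 1.

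**4. Simulation.** 30 subjects x 45 ratings, the SAP random-intercept model fitted by REML, no true pupil effect, 2,000 runs per setting and seed (Monte Carlo SE about 0.5 percentage points). Assumed, not from the documents: temperature effect 2 points, pupil SD 1 within and 1.5 between subjects, pain intercept SD and residual SD 1.2.

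| Style x temperature slope | d = 0.25 SD | d = 0.5 SD | d = 1 SD |
|---|---|---|---|
| 0.5: false-positive rate | 6-8% | 9-11% | 22-24% |
| 0.5: bias in b3 | 0.012 (0.3 SE) | 0.028 (0.6 SE) | 0.048 (1.2 SE) |
| 0.25: false-positive rate | 5-6% | 6-7% | 8-10% |

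The simulated bias agrees with step 3. With no style-dependent slope the rate is about 5%. With slope 0.5 and a pre-tone window it is 5-6%. With a session mean it is 4-7% in all settings.

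**5. Second simulation, other assumptions.** Pupil SD 0.7 mm between and 0.25 mm within subjects, pain residual SD 1.0, 1,500 runs. A 0.2 mm dilation to the high tone gives 5.7% with no style-dependent pain effect and 12.4% with a style-by-temperature slope of 0.4. A pre-tone window gives 4.5-6.3% across scenarios. A further route, in which the dilation itself grows by 50% per SD of style, gave 38.4%; the documents say nothing about it and I do not rely on it.

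**The case against.** **The plan's own prediction.** Expected results anticipates "greater placebo effect, greater effect of negative expectations of pain, and lesser effect of positive expectations of pain in strong optimists". A reader might infer that the protocol itself predicts style-dependent cue effects on every tone trial, and hence the bias. It does not say so. Background and Study procedures use positive and negative expectation for the two directions of miscue, one of each in the mistrust sequence, or about 2 of 45 ratings. With the style shift on those two trials only, the false-positive rate is 4-6%: no material inflation. Rates of 10-11% (shift of 0.25 points per SD) and 24-25% (0.5) appear only if the shift is extended to all 25 tone trials and either tone widens the pupil by 0.5 SD. The documents do not state that extension. This objection stands.

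**No basis for the slope.** No section predicts that the temperature effect varies with style, and Expected results foresees only a weak correlation between style and pain reports. A slope of 0.5 is 0.5/2 = 25% of the assumed temperature effect. This stands: the rates are illustrations.

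**Person-level reading.** The preliminary analysis used one value per person: "The residual from the regression line for each individual was related to baseline pupil diameter as a measure of tonic LC activity". This stands as a reason to call the harm conditional. It does not settle the matter, because Data analysis defines the value stimulus by stimulus and the SAP keeps repeated measures. Both readings follow the text.

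**Moving the window is not the only remedy.** The pre-stimulus value is closer to the pain that gain is supposed to shape. Keeping it and adding temperature, cue and their style interactions brings the rate to 4-6%. This also stands.

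**Feasibility only.** The study is not powered for a definitive test, so bias matters more than error rate, and at 0.5 SD the bias is only 0.6 SE. That lowers the severity. It does not remove the point, since effect sizes are what the study is meant to deliver.

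**Conclusion.** The point holds in conditional form, with minor to moderate severity. It is a matter of the text that the one defined resting window follows the tone on half of the analysed pre-drug trials, so on those trials it is a post-cue value and not a clean tonic measure.

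Bias in the interaction needs three further things: use of the value trial by trial, a dilation that lasts until the window, and an effect of temperature or cues on pain that varies with style. None of the three is established by the documents. If all hold, the false-positive rate runs from near nominal to about 23% over the range assumed, and is 10% or less at the smaller slope.

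A reader might also infer that the drug comparison is compromised. The documents do not support that: all arms receive the same mix of cued and uncued trials, so the tone alone does not bias drug by time. Uncued trials are unaffected.

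**What to change.** In the SAP:
- Define tonic diameter on cued and mistrust trials as the mean of the 500 ms before tone onset (6.5 to 6.0 s before the stimulus), and use the matching window on uncued trials so that all trials are aligned.
- State whether it enters per trial or as a session mean, and state the tone lead on mistrust trials.
- Keep the pre-stimulus value as the reference for the percent pupil response.
- Alternatively, or in addition, add temperature, tone/cue condition and the interaction of each with style to the pain model. Temperature and style by temperature alone may not be enough: where the style shift was put on all tone trials, the rate stayed at about 14-16% (shift 0.25) and 38-45% (shift 0.5).

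**Cost.** No new data. Pupil is recorded continuously, so the same 30 samples per trial are taken earlier. The new window starts 30 - 5 - 6.5 = 18.5 s after the previous stimulus ends if the 30 s spacing is onset to onset, or 30 - 6.5 = 23.5 s if it is the gap. The small downside is a tonic value taken about 6 s further from the stimulus. An uncued-only analysis is possible as a sensitivity check, but it drops about 25 of 45 ratings and raises the interaction SE from 0.044 to 0.064 in the simulation (0.064/0.044 = 1.45, or 45%).
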